## **I. Statement of Purpose**

The purpose of this pilot study is to prospectively identify operating room time delays, and assess the contributing impact of non-technical skills, team performance, and environmental factors in the operating room. This analysis will be used to identify root causes leading to delays and define areas for improvement.

## **II. Background and Rationale**

Time delays in the operating room play a role in increasing wait time length, number of cancelled cases, health care expenditure and resources. Furthermore, they inconvenience patients and families, and delay care. Minimally invasive surgery (laparoscopy) affords same-day discharge, faster recovery, and decreased morbidity. However, performing laparoscopy requires special equipment and multiple steps during set-up that can lead to time delays if not performed efficiently. Multiple factors have been identified to contribute to inefficient care delivery including (1): communication error, equipment failure, lack of teamwork among nursing, surgical or anesthesia teams, and duplication of tasks.

The Institute of Medicine (IOM) report “To err is human,” released in 2000, set off numerous studies to identify errors in healthcare and to develop strategies to avoid adverse outcome (2). The most commonly used types of interventions in surgery to date have been preoperative “surgical safety checklist” for aviation-style briefing (3-5). Other interventions have focused on training isolated components of non-technical skills, such as communication (6, 7).

The systems approach to human error is based on the assumption that human error is inevitable and looks for failures in the system rather than in the individual. This novel approach has led to the current concept of Crew Resource Management training as a strategy to enhance non-technical skills in order to avoid, trap and mitigate error and ultimately increase safety (8-10). This concept can be extended to the area of interest of time delays. Unanticipated events such as human resource absenteeism, equipment failure or malfunction, and unscheduled emergency add-on cases as examples, inevitably will arise

to cause time delays. These delays can occur in the OR directly, or in other areas of the hospital which can in turn affect the flow in the OR. Efficient use of the OR requires expert technical skills of the surgical team, but more importantly teamwork within the peri-operative team and administration that are prepared to accommodate an array of potential unforeseen circumstances that can lead to time delays. Understanding what are the most common types of delays, the frequency and trends in which they occur, and the root causes for the delays can help prevent delay by being prepared, that is, anticipating delay possibilities and having a plan in place to minimize delay. Although factors outside of the OR can influence the intra-operative period, this study focuses specifically on determining which factors within the OR can be targeted to improve efficiency.

An innovative technology, the OR Black Box, has been developed for the OR to mimic the blackbox in airline industry. It has the ability to record the surgical field, the anesthetic equipment, and the level of noise in the OR. This technology also has the ability to time stamp all activities that take place in the OR. Using this technology, we will be able to record all of the important check points that take place in the course of a complex laparoscopic procedure (i.e. total laparoscopic hysterectomy). This will in turn highlight several potential areas for examining efficiency that can be generalized to other surgical specialities. This analysis will be used to identify root cause(s) leading to OR delays and define areas for improvement. The causes of delays can be reported to the team members through formative performance-based feedback (11).

### *Summary*

OR delays are a result of a chain of events spanning multiple phases of operative patient care. Currently, there are no reported methods available to objectively observe and evaluate causes for OR efficiency including non-technical skills factors. Delays are tracked by the nursing staff which is a subjective process fraught with inconsistency and associated biases. Objective measures of intra-operative OR delays, identification of their root causes, and creation of an intervention to improve OR efficiency has the potential for the development of a standardized framework to minimize OR efficiency, which could be generalized to any surgical discipline to improve OR efficiency.

### **III. Research Objectives**

- 1) To prospectively identify patterns or chain of events leading to prolonged case duration in total laparoscopic hysterectomy procedure in a gynecologic surgical population.
- 2) To assess how non-technical skills and team performance of surgeon, nursing and anesthesiology teams correlate with case duration and subsequent cancellations.

### **IV. Hypothesis & Novelty**

We hypothesize that non-technical skills and teamwork in the OR are correlated with operating room efficiency. Furthermore, we hypothesize that time delays can be tracked to a chain of events that is influenced by non-technical skills as well as environmental factors in addition to technical skills. Together, this knowledge can be used to identify areas for organizational, technological, and team or individual improvement, and to design a standardized framework to improve individual and team performance and ultimately increase OR efficiency that can be applied to any surgical department. The novelty of this approach is the prospective assessment of non-technical, team performance, and environmental factors in the OR as well as delays, inefficiencies, and patient outcome in order to identify areas for improvement and characterize a chain of events.

### **V. Methods**

#### **Experimental Design**

1. Prospective observational study
2. Randomized trial (Sub-study/branch of pilot study: Measuring the impact of standardized efficiency framework to optimize OR utilization)

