#### **General Design**

##### *Study Subjects*

A minimum of sixty elective total laparoscopic hysterectomy procedures performed in one operating room of an academic tertiary care center during a twelve-month period will be included in this study. Procedures will only be excluded if data collection is in any part

incomplete or patient or OR staff consent was declined or withdrawn. Studying total laparoscopic hysterectomy was selected as a marker to analyze OR efficiency as this is a commonly performed procedure that requires moderate degree of complexity in equipment set-up and can be generalized to other laparoscopic procedures. Health professionals that will be participating in the study are OR nursing staff, technical (scrub) assistants, anesthesia staff, and surgeons. The nursing team involved in each procedure typically consists of one scrub technical assistant or nurse and one circulating nurse. The anesthesia team is typically represented by either a staff anesthesiologist or an anesthesia resident (who is always supervised by a staff anesthesiologist). The surgical team is comprised of the staff surgeon, and two other surgeons, typically a fellow and a surgical resident. The staff surgeon will be present during all cases and perform the majority of procedures however, some full procedures, or particular steps of procedures, will be performed by a clinical fellow or a surgical resident under staff surgeon's direct supervision, which is standard practice in teaching hospitals. Medical students will occasionally also be part of the surgical OR team as part of their surgical rotation during clinical clerkships.

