#### *Recruitment of surgical staff*

The project investigator as well as the participating staff surgeons in the Department of Gynecologic Surgery at St. Michael's Hospital will be study subjects in all observed procedures, and therefore will also sign the written informed consent. All gynecology surgical staff (including fellows and trainees) will be initially contacted about the study via e-mail and will be invited to attend an informative presentation at the next Grand Rounds session (see Appendix 1). Surgical residents will be contacted via e-mail by the Program Director's office. Occasionally, medical students participate in the unit's OR for clinical clerkships. The rotation plan of surgical clerkship students is known to the undergraduate medical education coordinator for Fitzgerald academy, St. Michael's Hospital, medical students scheduled for the unit's OR lists will be contacted through the medical student speaker as a student representative. Informed consent will be obtained from all surgical staff who wish to participate in the study. This will be obtained by the Research Coordinator at the end of the Grand Rounds presentation. Prior to the day of scheduled surgery, a reminder email will be sent to all staff who have not yet provided informed consent or who were unable to attend the Grand Rounds presentation.

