#### *Declined or withdrawn consent*

The informed consent of all participants (patients, healthcare staff, residents and students) has the highest priority for the researchers. If any team member in the OR has not given consent or has previously withdrawn consent, the procedure will not be recorded. If a staff member agrees, he or she may be scheduled for a different OR. To ensure that all members of the operating team have given consent, the Research Coordinator will monitor the OR lists and staff schedules one day prior to the list to ensure valid informed consent is available of all team members scheduled for that day. For that purpose, the Research

Coordinator will keep a master log that contains all names and roles of participants that have given informed consent (Appendix 7). If an OR team member has not given valid consent or has withdrawn consent, the Research Coordinator will ensure that on that particular day no recording is made. Consent of staff members will be valid for 12 months. This is explained in the staff consent form. Every study participant can withdraw consent at any point in time during the study. If a participating staff member withdraws consent, no procedures will be recorded from that point on, if the respective staff member is present. A patient participating in the study can also withdraw consent at any point before her procedure. Both staff members and patients can withdraw consent for procedures that have already been recorded, if they do so within 48 hours of the procedure. In order to maintain the scientific integrity of the study and avoid bias, the recordings may not be withdrawn beyond the 48-hour timeframe, nor may the other data collected up to the point of withdrawal. Data from procedures that have already been video-audio recorded *and evaluated* while valid consent existed cannot be withdrawn. This is a requirement to maintain the scientific integrity of the study and this will be clarified in the consent forms.

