#### *Hawthorne effect*

The Hawthorne effect describes a phenomenon of an unintentional change in behavior in response to the presence of an observer. The Hawthorne effect can affect any study that involves observation of the study subjects and can therefore not be completely eliminated (12). It is known that the Hawthorne effect typically fades with time, as the subjects are getting used to the observation, especially if the presence of an observer is not directly visible. Two factors may reduce the Hawthorne effect in our study: 1) long duration of the study over 12 months, which is likely to lead to an acclimatization of the subjects once the novelty of the cameras wears off. 2) Video recordings will be made with small surveillance cameras that are mounted on the wall. The unobtrusive nature of the observation is likely going to accelerate the habituation, further reducing the Hawthorne effect.

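### Do the twelve-month window, the staff consent term and the shared surgeons leave the randomized branch no sound time to run?

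*Protocol*

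**What the plan says.** Experimental Design has two items: a prospective observational study, and a "Randomized trial (Sub-study/branch of pilot study: Measuring the impact of standardized efficiency framework to optimize OR utilization". No other section gives the second item arms, an allocation unit, a sample, a start or a period. Research Objectives, Primary Outcome Measure and Statistical Analysis all concern the observational study, and Statistical Analysis describes the work as observational and as a pilot.

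The fixed quantities are these:

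- Under Study Subjects, the sample is set as follows: "A minimum of sixty elective total laparoscopic hysterectomy procedures performed in one operating room of an academic tertiary care center during a twelve-month period".
- Hawthorne effect: a "long duration of the study over 12 months" is one of two reasons given for expecting staff to get used to the cameras.
- Declined or withdrawn consent: "Consent of staff members will be valid for 12 months". If a team member lacks valid consent, the Research Coordinator "will ensure that on that particular day no recording is made".
- Recruitment of surgical staff: the investigator and the participating staff surgeons "will be study subjects in all observed procedures".

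On where the framework comes from, Hypothesis & Novelty says the knowledge gained can be used "to design a standardized framework to improve individual and team performance and ultimately increase OR efficiency". The Summary in the background section mentions "creation of an intervention to improve OR efficiency" among the steps with potential value. Relevance says in similar terms that measuring delays can lead to such a framework.

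**The concern.** If the framework is built from the observational findings, its trial has to follow the cohort. The cohort appears to occupy the whole twelve months, and a surgeon who consented at the start is out of consent by month 12. Cases with that surgeon could then not be recorded, and the protocol text describes no renewal. A later branch would therefore lie outside both the study period and the consents.

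Running the branch inside the twelve months seems no better. The framework would not yet have been derived from the data. The same surgeons, in one operating room, could treat cases in both arms of a trial of something meant to change how they work. What they learn would carry into control cases and shrink the measured effect. Framework cases could also enter the delay incidence that is the primary outcome.

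At stake would be a randomized comparison that is either unrecordable or biased toward no effect, and possibly a contaminated primary outcome.

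**Working it through.** **Inputs from the protocol.** At least 60 procedures, one operating room, twelve months (Study Subjects); 12-month staff consent (Declined or withdrawn consent). No accrual rate, alpha, power, effect size or allocation ratio is given, and Statistical Analysis says no prior power or sample size calculation can be done. The figure of sixty therefore cannot be reproduced by a formula.

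**Timing.** Months to reach sixty = 60/rate; months left = 12 − 60/rate; cases possible in them = rate × months left. Only the first rate comes from the protocol (60/12 = 5); the others are assumed.

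| Cases per month | Months to 60 | Months left | Cases in the months left |
|---|---|---|---|
| 5 | 12 | 0 | 0 |
| 6 | 10 | 2 | 12 |
| 8 | 7.5 | 4.5 | 36 |
| 10 | 6 | 6 | 60 |
| 12 | 5 | 7 | 84 |

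The months left assume that the cohort closes at sixty, and they are counted before any time to analyse the data and build the framework. A sequential branch within the window is impossible at the minimum pace and is not excluded at faster ones. Beyond the window, an assumed 30 to 60 further procedures at 5 a month would take 30/5 = 6 to 60/5 = 12 more months. That breaks the plan only if the twelve months bind the branch and consent cannot be renewed. The protocol states neither.

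**Carry-over.** Suppose half of control procedures are delayed, the framework cuts that by a fraction r, a fraction c of the effect reaches control cases, and sixty cases are split 30/30. All four are assumptions.

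- Observed difference = 0.5 × r × (1 − c).
- 95% half-width = 1.96 × √[(pc(1 − pc) + pf(1 − pf))/30], where pc = 0.5 − 0.5rc and pf = 0.5 − 0.5r.

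| r | c | Observed difference | 95% half-width |
|---|---|---|---|
| 0.3 | 0 | 15.0 points | 24.7 points |
| 0.3 | 0.25 | 11.3 points | 24.7 points |
| 0.3 | 0.5 | 7.5 points | 24.6 points |
| 0.5 | 0 | 25.0 points | 23.7 points |
| 0.5 | 0.25 | 18.8 points | 23.6 points |
| 0.5 | 0.5 | 12.5 points | 23.2 points |

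The arithmetic is sound, but it does not describe this trial. The protocol gives no allocation unit, so c is unknown and may be zero. Nor is a delayed procedure the branch's stated target: Experimental Design names OR utilization, which Primary Outcome Measure defines as a ratio of canceled to completed cases.

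**The passages side by side.**

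- *Order.* Hypothesis & Novelty and Relevance say what the findings can be used for or can lead to. These are aims and set no schedule.
- *Period.* Study Subjects describes the procedures to be included, and the Hawthorne effect section makes a point about habituation. Neither mentions the branch.
- *Consent.* Recording is barred where valid consent is absent, and a renewed consent would be valid. The section refers to the staff consent form for the 12-month term, and that form is not in the text available. Staff who join later also have later expiry dates.
- *Shared surgeons.* The text speaks of several staff surgeons in the observed procedures and says nothing about arms. Allocation by surgeon or by period is not excluded.

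**The case for a change.** The strongest reply is that sixty is a minimum and not a stopping point. No text closes the cohort at sixty, so faster accrual may add cohort cases without freeing any months. No other period is given for the branch, and no renewal of consent is described. Design, period and consent term belong in a protocol, so an unseen analysis plan does not supply them. With one operating room and shared nursing and anesthesia staff, allocation by surgeon or period would still separate the arms poorly.

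Much of this stands as an account of what is missing. The protocol names a randomized branch and gives it no place in the timeline, the sample or the consent term. But silence about a period or a renewal is not a rule against either. Objectives, outcomes and statistics that are confined to the observational study fit a branch with its own later arrangements at least as well as one squeezed into this window. The reference to an observational study in Statistical Analysis can simply mean the first item under Experimental Design, so no contradiction is shown there. Weak separation of arms is a matter of allocation, to be settled when the branch is designed, and it does not show that no timing works.

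**Conclusion.** No change to the plan is called for. The protocol does not show that the randomized branch cannot be run soundly, that it overlaps the cohort, or that its effect would be diluted. Zero months left holds only at 5 cases a month; at assumed rates of 6 to 12 a month, 2 to 7 months would remain if the cohort closed at sixty. The fall from 15 to 7.5 points, or from 25 to 12.5, rests on an assumed delay rate, effect, split and carry-over, and on an outcome other than the one named for the branch.

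What remains is missing detail: one line names a trial that the rest of the document does not describe. The delay incidence and the correlation and regression analyses belong to the observational study, and nothing shown disturbs them. Deleting the line or referring it to a separate protocol would tidy the text without altering any result. A longer period, a new consent round, or a second team or operating room would cost time and resources to settle a design that this document does not yet set out.

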#### **General Design**

##### *Study Subjects*

A minimum of sixty elective total laparoscopic hysterectomy procedures performed in one operating room of an academic tertiary care center during a twelve-month period will be included in this study. Procedures will only be excluded if data collection is in any part

incomplete or patient or OR staff consent was declined or withdrawn. Studying total laparoscopic hysterectomy was selected as a marker to analyze OR efficiency as this is a commonly performed procedure that requires moderate degree of complexity in equipment set-up and can be generalized to other laparoscopic procedures. Health professionals that will be participating in the study are OR nursing staff, technical (scrub) assistants, anesthesia staff, and surgeons. The nursing team involved in each procedure typically consists of one scrub technical assistant or nurse and one circulating nurse. The anesthesia team is typically represented by either a staff anesthesiologist or an anesthesia resident (who is always supervised by a staff anesthesiologist). The surgical team is comprised of the staff surgeon, and two other surgeons, typically a fellow and a surgical resident. The staff surgeon will be present during all cases and perform the majority of procedures however, some full procedures, or particular steps of procedures, will be performed by a clinical fellow or a surgical resident under staff surgeon's direct supervision, which is standard practice in teaching hospitals. Medical students will occasionally also be part of the surgical OR team as part of their surgical rotation during clinical clerkships.

#### *Recruitment and consent of patients*

All patients that are scheduled for elective surgery will be eligible for participation in the study. Minors and patients with mental disability or impairment are not eligible for the study. Pregnant women will also not be enrolled. All eligible patients will be informed about the study by the treating surgeon during their appointment in the clinics. Each patient will then receive written information (see Patient Consent form) to read at home in order to provide adequate time for consideration. All patients that have been scheduled for surgery routinely return for a second presentation for a consult with Anesthesiology, this is typically two to three weeks prior to the surgery. Upon this pre-admission appointment, the Research Coordinator, who is not involved in patient treatment, will provide additional information regarding the details of the study to the patients and will obtain informed consent. Patients that are scheduled for elective total laparoscopic hysterectomy surgery will be enrolled in the study, provided that informed consent has been obtained. It is furthermore important to note that participation in the study will not result in any deviation

of the standard treatment of patients in our unit. This includes all visits prior to the procedure, the surgery and hospital stay, and postoperative care.

#### *Recruitment of nursing staff*

Prior to the start of the study, approval will be obtained from the clinical manager of perioperative services (OR leader). Nursing staff will be identified through the roster and addressed by the Clinical Leader Managers of Perioperative Services, via their St. Michael's Hospital email addresses. All nursing staff scheduled to work with this unit will be invited by the clinical manager via email to attend an informative presentation given by one of the researchers (see Appendix 1). After the presentation, the Research Coordinator will then obtain written informed consent. All staff members who did not have the opportunity to attend the presentation will be informed of the study by the Research Coordinator. Nursing students are occasionally scheduled in the unit's OR, mostly to observe the procedure for training purposes (i.e., not active participants). Nursing students who are scheduled to attend one of the unit's OR lists will be informed of the study by the Nurse Educator and informed consent will be obtained by the Research Coordinator. If any member of the staff declines consent or withdraws consent at any point during the study, procedures involving that staff member will not be recorded from that point on. A reminder e-mail will be sent to staff who are scheduled in the OR but who did not provide informed consent or were unable to attend the Grand Rounds presentation (see "E-mail consent reminder"). This e-mail will remind them of the study and provide another opportunity to sign the consent form if they wish to participate.

